10.1.1.15 Visit 15/ Week 144/ Month 36 (Day 1009 ± 7)

- Collect adverse events
- Record concomitant medication
- Take vital signs including heart rate and blood pressure
- Get body weight measurement
- Physical examination
- Review patient's diet. Patient should be on a NCEP-ATPIII TLC diet or equivalent.
- Data collection on IMP administration and IMP compliance check by review of diary and treatment kit
- Obtain fasting blood sample for:
 - Lipids: measure and/or calculation of total-C, LDL-C, HDL-C, TG, non-HDL-C, Apo B, Apo A-1, ratio Apo B/Apo A-1, and Lp (a)
 - Hematology
 - Chemistry
 - CPK
 - Liver panel
 - Anti-alirocumab antibodies
- Local urine pregnancy test (females of childbearing potential only).
- IVRS/IWRS contact for allocation of a batch number for treatment kit
- IMP kit dispensation and treatment administration package should be provided. The patient injection instruction manual and diary may be given, as needed.
- Reminders

- An appointment will be given for the next visit.
- Patient to bring the diary and used kits and unused auto-injectors at the next visit.

10.1.1.16 Visit 16/ Week 156 (Day 1093 ± 7)

- Collect adverse events
- Record concomitant medication
- Data collection on IMP administration and IMP compliance check by review of diary and treatment kit.
- IVRS/IWRS contact for allocation of a batch number for treatment kit
- IMP kit dispensation and treatment administration package should be provided. The patient injection instruction manual and diary may be given, as needed.
- Reminders
 - An appointment will be given for the next visit.
 - Patient to bring the diary and used kits and unused auto-injectors at the next visit
 - Remind patient to be in fasting conditions (ie, overnight, at least 10-12 hours fast and refrain from smoking) for next visit. Alcohol consumption within 48 hours and intense physical exercise within 24 hours preceding the next visit are discouraged.

10.1.1.17 End-of-treatment visit: Visit 17/ Week 168/ Month 40 (Day 1177± 7)

The end of study is scheduled to be in second quarter 2017 or when the drug will become commercially available for the patient in the respective country whatever comes first. Thus, the End-of-treatment visit might be performed earlier than on Week 168 according to the date of inclusion of each patient in the OLE study, or if the patient early discontinues the study.

- Collect adverse events
- Record concomitant medication
- Take vital signs including heart rate and blood pressure
- Get body weight measurement
- Physical examination
- Review patient's diet. Patient should be on a NCEP-ATPIII TLC diet or equivalent.
- Data collection on IMP administration and IMP compliance check by review of diary and treatment kit
- IVRS/IWRS contact to document the end of treatment
- Obtain fasting blood sample for:
 - Lipids: measure and/or calculation of total-C, LDL-C, HDL-C, TG, non-HDL-C, Apo B, Apo A-1, ratio Apo B/Apo A-1, and Lp (a)

- Hematology
- Chemistry
- CPK
- Liver panel
- Anti-alirocumab antibodies

- Local urine pregnancy test (females of childbearing potential only).
- Completion of EQ-5D questionnaire by patient.
- Reminders
 - For all the patients, those who prematurely discontinue the treatment irrespective of the reason and those who will complete the study, an appointment will be given for the Follow up call. This phone call will have to be scheduled 10 weeks after last injection (+/- 7 days).

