6 STUDY DESIGN

6.1 DESCRIPTION OF THE PROTOCOL

This is a multicenter, multinational, Phase 3, open-label extension, uncontrolled study to assess the long-term safety and efficacy of alirocumab, when added to currently available LMT, in heFH patients previously participating in the ODYSSEY FH I, ODYSSEY FH II, ODYSSEY High FH or ODYSSEY Long Term studies.

Patients must have been diagnosed with heFH in the parent study, have completed one of the above parent studies, and be willing to participate in the ODYSSEY OLE study. Patients who missed the last injection or who performed the end of treatment visit outside the expected timelines can also be enrolled.

The visit 1 (Day 1) of the ODYSSEY OLE study corresponds to:

- the end of treatment visit of the Double-Blind Treatment Period for the patients enrolled in one of the three following parent studies ODYSSEY FH I, ODYSSEY FH II, ODYSSEY High FH.
- the end of study visit, after the 8 week follow-up period, for the patients having participated in the ODYSSEY Long Term study.

Patients who meet eligibility criteria at the visit 1 (Day 1) will receive the first SC injection of alirocumab in the clinic on the same day.

In addition, patients from the ODYSSEY Long Term study will have the possibility to perform a placebo, self-injection training, before the first alirocumab administration using an auto-injector on that same day (Day 1), as they used a different device (a prefilled syringe) in the parent study.

At entry in the ODYSSEY OLE study, visit 1 on Day 1:

- All eligible patients from ODYSSEY High FH will get the alirocumab 150 mg dose.
- All eligible patients from ODYSSEY FH I, ODYSSEY FH II and ODYSSEY Long Term will get alirocumab 75 mg.

From Week 12 (Visit 4), the Investigator will manage, based on his/her own judgment and LDL-C values, adjustment of alirocumab doses (either up-titration from 75 to 150 mg every 2 weeks or down-titration from 150 to 75 mg every 2 weeks, or maintenance of the dose, will be possible).

The study consists of:

- An open-label treatment period with alirocumab of up to 168 weeks, ie approximately 3.5 years, for the first patients enrolled, or until the product becomes commercially available for the patient in the country, whatever comes first.
- A post-treatment safety follow up period of 10 week-duration after last IMP injection for all the patients, the patients who will complete the study and the patients who will early discontinue whatever the reason.

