6.2 DURATION OF STUDY PARTICIPATION

6.2.1 Duration of study participation for each patient

The OLE study is planned to be completed in second quarter 2017 which corresponds to a study duration of approximately 168 weeks for the first patients enrolled or until the drug is commercially available for the patient in the respective country, whatever comes first. For patients in the UK, the study will last a maximum of 176 weeks.

The study duration includes up to approximately 3.5 years of treatment for the first patients enrolled, and 10 weeks of follow up after the last IMP injection for all the patients, those who will complete the study and those who will early discontinue whatever the reason.

The study will be considered as completed for a patient in the following situations:

- When the alirocumab is commercially available in the patient's country
- In second quarter 2017, if alirocumab is not yet commercially available in the patient's country

An EOT visit will be done 2 weeks after the last IMP injection and a safety follow up call 10 weeks after the last IMP injection.

The following situations will be considered as premature discontinuation of the patient from the study:

- Any withdrawal from the study to switch to an anti-PCSK9 inhibitor different from commercial alirocumab
- Any other reason

An unscheduled visit should take place within 5 days after the last IMP administration if possible, with assessments normally planned at the EOT visit, and a safety follow up call performed 10 weeks after the last IMP injection (see section 10.3.4).

The end of study per patient is the last protocol planned call. Patients with a Serious Adverse Events (SAEs) or an Adverse Event of Special Interest (AESI) should be followed until resolution, stabilization, or death.

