10 STUDY PROCEDURES

For all visits after Day 1/Week 0 (first visit), a time window of \pm 7 days during the whole treatment period, including the follow-up call as applicable) will be allowed.

For all visits after Day 1/first visit, if one visit date is changed, then the next visit should take place according to the original schedule as outlined Section 1.2.

Blood samplings:

The blood sampling for determination of lipid parameters (ie, total-C, LDL-C, HDL-C, TG, non-HDL-C, Apo B, Apo A-1, ratio Apo B/Apo A-1, Lp [a]) should be performed in the morning, in fasting condition (ie overnight, at least 10-12 hours fast and refrain from smoking) for all site visits requiring blood sampling throughout the study. Alcohol consumption within 48 hours and intense physical exercise within 24 hours preceding the blood sampling are discouraged.

Note: if the patient is not in fasting conditions, the blood sample will not be collected and a new appointment will be given the closest as possible to the date of this visit) to the patient with instruction to be fasted (see above conditions).

Laboratory tests:

The laboratory data are collected in accordance with the study schedule in Section 1.2 and forwarded to the central laboratory:

- Hematology: blood cell count including hematocrit, hemoglobin, red blood cell count, red blood cell distribution width, reticulocyte count, white blood cell count with differential count and platelets
- Chemistry: glucose, sodium, potassium, chloride, bicarbonate, calcium, phosphorous, urea nitrogen, creatinine, uric acid, total protein, LDH, albumin, and γGT
- Liver panel: ALT, AST, ALP, and total bilirubin; in case of total bilirubin values above the normal range, differentiation into conjugated and non-conjugated bilirubin will occur automatically.
- Creatine Phosphokinase (CPK).
- Local urine pregnancy test.

Decision trees for the management of certain laboratory abnormalities by Sanofi are provided in Appendix C and Appendix D.

Anti-alirocumab antibody samples: see section 9.3.1.

Physical examination:

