10.1.2 Post-treatment Follow up period

End of Study Phone call: Visit 18/ Week 176 (\pm 7 days)

This phone call is to be done for all the patients, those who discontinue the treatment prematurely, whatever the reason, and those who will complete the study, and will take place approximately 10 weeks after the last injection of alirocumab.

- Collect adverse events
- Record concomitant medication, including any commercially available PCSK9 inhibitor different from alirocumab
- IVRS/IWRS contact to document the end of study

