10.3.4 Handling of patients after permanent treatment discontinuation

Patients who prematurely discontinue study treatment (regardless of the reason) should undergo an unscheduled visit with assessments normally planned at the end of treatment visit (it should take place within 5 days of treatment discontinuation, if possible).

The patient, at a minimum, should then be followed up for at least 10 weeks from last study treatment administration or up to recovery or stabilization of any AE to be followed-up as specified in this protocol, whichever comes last.

A final End of Study phone call will take place with assessments at 10 weeks after the premature treatment discontinuation.

All definitive discontinuation of study treatment should be recorded by the Investigator in the appropriate screens of the e-CRF and in the patient's medical records when considered as confirmed. IVRS/IWRS should be notified when a patient prematurely discontinues study treatment.

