10.4.2 General guidelines for reporting adverse events

• All AEs, regardless of seriousness or relationship to IMP, spanning from the signature of the informed consent form of the current study until the end of the study as defined by the protocol for that patient, are to be recorded on the corresponding screen(s) of the e-CRF.

- Whenever possible, diagnosis or single syndrome should be reported instead of symptoms. The Investigator should specify the date of onset, intensity, action taken with respect to IMP, corrective treatment/therapy given, additional investigations performed, outcome, and his/her opinion as to whether there is a reasonable possibility that the AE was caused by the IMP.
- The Investigator should take appropriate measures to follow all AEs until clinical recovery is complete and laboratory results have returned to normal, or until progression has been stabilized, or until death, in order to ensure the safety of the patients. This may imply that observations will continue beyond the last planned visit per protocol, and that additional investigations may be requested by the monitoring team up to as noticed by the Sponsor.
- When treatment is prematurely discontinued, the patient's observations will continue until the end of the study as defined by the protocol for that patient.
- Laboratory, vital signs or ECG abnormalities are to be recorded as AEs only if:
 - Symptomatic and/or
 - Requiring either corrective treatment or consultation, and/or
 - Leading to IMP discontinuation or modification of dosing, and/or
 - Fulfilling a seriousness criterion, and/or
 - Defined as an AESI

See Appendix B for a summary of AE reporting guidelines.

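### The final safety call may come up to 7 days before the 70-day treatment-emergent period ends, so a little unobserved time is counted as event-free

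*Protocol*

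**What the plan says.** Days below are counted from the last injection unless stated otherwise.

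**Timing of the call.** The end-of-treatment section (Protocol 10.1.1.17) states: "This phone call will have to be scheduled 10 weeks after last injection (+/- 7 days". This applies both to completers and to patients who stop early. The flow chart (1.2) gives Visit 18 the same tolerance, and Protocol 10 extends the 7-day window to visits "during the whole treatment period, including the follow-up call as applicable". Section 10.1.2 repeats the window and says that the call "will take place approximately 10 weeks after the last injection of alirocumab".

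**What the call ends.** Under Protocol 6.2.1, "The end of study per patient is the last protocol planned call". New adverse events are recorded "until the end of the study as defined by the protocol for that patient" (10.4.2). SAP 2.1.4.1 likewise stops recording at the end of study.

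**What runs to Day 70.** Protocol 9.1 and SAP 2.1.4 close the treatment-emergent (TEAE) period 70 days after the last dose, because residual drug effect is expected for that long. SAP 2.4.5.1 credits event-free patients with the whole TEAE period in the event rates, and censors them at its end in the Kaplan-Meier analyses.

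**Intended follow-up.** Protocol 6.1 describes "A post-treatment safety follow up period of 10 week-duration after last IMP injection for all the patients". For patients who stop early, 10.3.4 says that they should be "followed up for at least 10 weeks from last study treatment administration".

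**The concern.** At an ordinary visit a symmetric window does no harm, because the next visit picks up whatever happened in between. Visit 18 has no next visit. If the call is made on Day 63 to 69, new events in the remaining days are no longer routinely recorded, but the analysis still treats those days as observed and event-free. Any error goes one way, towards lower adverse event rates, and safety is the primary endpoint.

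The definitions also stop fitting together. The post-treatment period starts the day after the TEAE period and runs to the end of study. For a patient called early it would end before it began.

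**Working it through.** **1. Reproduce the schedule.** The end-of-treatment visit at Week 168 is 2 weeks after the last injection, so that injection is at Week 166. Week 166 + 10 = Week 176, which is the week given for Visit 18.

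**2. Window.** 10 weeks × 7 = 70 days. Earliest call: 70 − 7 = Day 63. Latest call: 70 + 7 = Day 77. SAP 2.2 calls follow-up insufficient only below 9 weeks, and 9 × 7 = 63, so no in-window call is flagged.

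**3. Gap.** Unobserved days = 70 − day of call:

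| Call on Day | 63 | 64 | 65 | 66 | 67 | 68 | 69 | 70–77 |
|---|---|---|---|---|---|---|---|---|
| Days unobserved | 7 | 6 | 5 | 4 | 3 | 2 | 1 | 0 |

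**4. Largest share of the TEAE period.** With the first injection as study day 1, the period ends on study day 1 + 7 × (week of last injection) + 70.

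| Last injection | TEAE period (days) | Largest gap |
|---|---|---|
| Week 166 (full duration) | 1 + 1,162 + 70 = 1,233 | 7/1,233 = 0.6% |
| Week 22 (illustration) | 1 + 154 + 70 = 225 | 7/225 = 3.1% |
| Single dose (illustration) | 1 + 0 + 70 = 71 | 7/71 = 9.9% |

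**5. Person-time.** The documents do not say when calls were made, so only a range can be given. If all calls fall on Day 70 to 77, the overcount is 0. If all fall on Day 63, it is 100 × 7 / 365.25 = 1.9 patient-years per 100 patients. For 100 full-duration patients the total is 100 × 1,233 / 365.25 = 337.6 patient-years.

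**6. What is missed after an early call.**

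| Event between the call and Day 70 | Still captured? |
|---|---|
| Death | Yes, reported as post-study (Protocol 9.1); also on-treatment under SAP 2.1.4.2 |
| Serious event judged related | Yes, if it reaches the investigator (Protocol 10.4.3) |
| Event already open at the call | Yes, followed up (Protocol 6.2.1, 10.4.2) |
| New non-serious event | Not routinely |
| New non-fatal serious event judged unrelated | Not routinely |

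**7. Synopsis wording.** The assessment schedule equates the 10 weeks with 8 weeks after the end-of-treatment visit, for completers and early discontinuers alike. For completers, 14 + 56 = 70, which agrees. For an early discontinuer seen within 5 days of the last administration (6.2.1), it gives Day 5 + 56 = 61 at the latest, which is before even the earliest day of the window.

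**The case against.** **The tolerance looks deliberate.** Every visit after Day 1 has the same 7 days, 10.1.2 speaks only of an approximate 10 weeks, and the SAP's 9-week limit is exactly the lower edge of the window. This stands as an explanation of how the window arose. It does not close the gap, because the 9-week limit is only a disposition flag and leaves both the TEAE period and the censoring rule unchanged. Elsewhere the SAP does tie time at risk to observation: analyses of time to a laboratory or vital-sign abnormality censor at the last assessment (2.4.5.3, 2.4.5.4), and at an interim analysis the TEAE period of ongoing patients stops at the cut-off (section 3).

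**Early discontinuers have extra protection.** Section 10.3.4 sets them a 10-week minimum, so a call before Day 70 cannot simply be called compliant for them. This largely stands. Since 10.1.1.17 expressly gives these patients the 7-day window too, sites have two conflicting instructions. It does mean that the larger percentages for short exposure describe mainly patients for whom the plan already asks for more, and they should not be read as typical.

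**Little of clinical weight is lost.** This also stands, as the table of events shows. A reader might infer that deaths or drug-related serious events go missing, but the documents provide for both. A death after an early call but by Day 70 counts as on-treatment and post-study but not on-study, so only its label is affected.

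**The censoring rule is wider than this window.** It also applies to patients with no follow-up call at all. That is correct. SAP 2.2 at least counts those patients as having insufficient follow-up, which it does not do for a call on Day 63 to 69.

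**Conclusion.** The inconsistency is real and minor. The plan permits up to 7 days per patient to be counted as event-free without observation. This falls short of the 10-week follow-up in Protocol 6.1 and conflicts with the 10-week minimum for early discontinuers in 10.3.4. The ceiling is 0.6% of TEAE time for a full-duration completer. It is a larger share after short exposure, and zero where calls fall on Day 70 to 77.

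A reader might go further and infer that the adverse event rates are materially understated, or that a large fraction of calls come early. The documents support neither. They permit an early call but say nothing about how often one is made, and the ceiling is small for long-treated patients.

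The conclusion assumes that sites use the window as written, and that recording of new events stops on the day of the call, as 6.2.1 and 10.4.2 together imply.

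**What to change.** 1. **Protocol 1.2, 10, 10.1.1.17 and 10.1.2:** set the Visit 18 window to 0 to +7 days, ie Day 70 to 77. Every in-window call then covers the TEAE period. Full-duration UK patients are capped at 176 weeks (6.2.1), and Week 166 + 10 already reaches Week 176, so aim for Day 70 in that group. No injection needs to be given up.
2. **SAP 2.4.5.1:** where the call was made before Day 70, end event-free person-time and Kaplan-Meier censoring for adverse events at the earlier of the call and last injection + 70 days. Still count any event or death reported up to Day 70 as treatment-emergent or on-treatment. This corrects the credited time for calls already made but does not recover events that were never recorded.
3. **Protocol synopsis, assessment schedule:** limit the equivalence with 8 weeks after the end-of-treatment visit to completers.

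The closing sentence of 10.3.4 ("A final End of Study phone call will take place with assessments at 10 weeks after the premature treatment discontinuation") can stay. Discontinuation would normally fall on or after the last injection, so re-anchoring that sentence to the injection could move calls earlier.

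**Cost.** A small protocol amendment with ethics review at about 200 sites, a short SAP addition, some calls up to 7 days later, and slightly less person-time. Day 70 to 77 lies inside the present window, so sites can be asked to use it before the amendment takes effect.

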10.1.2 Post-treatment Follow up period

End of Study Phone call: Visit 18/ Week 176 (\pm 7 days)

This phone call is to be done for all the patients, those who discontinue the treatment prematurely, whatever the reason, and those who will complete the study, and will take place approximately 10 weeks after the last injection of alirocumab.

- Collect adverse events
- Record concomitant medication, including any commercially available PCSK9 inhibitor different from alirocumab
- IVRS/IWRS contact to document the end of study

10.2 DEFINITION OF SOURCE DATA

Evaluations that are reported in the e-CRF must be supported by appropriately signed identified source documentation related but not limited to the following:

- Agreement, date, and signature of informed consent mentioning the study identification.
- Patient identification, last participation in a clinical trial, medical history, associated diseases, and data related to the studied pathology.
- Contraception methods for women of childbearing potential.
- Previous and concomitant medication (including the lipid modifying therapy).
- Study identification.
- Treatment number, dates of administration.

- Dates of visits and assessments including the examination report.
- Vital signs, height, body weight.
- Faxed central lab reports (dated and signed by the Principal Investigator or Sub-Investigator).
- IVRS/IWRS confirmation fax (training kit allocation, treatment reallocation, discontinuation, end of open label extension period, end of study).
- Adverse events and follow-up:
 - In case of SAE, the site should file in the source document at least copies of the hospitalization reports and any relevant examination reports documenting the follow-up of the SAE.
- Date of premature study discontinuation (if any) and reason.

Source documentation may be found in the following:

- Patient's identity.
- Medical history.
- Hospital records.
- Nursing notes.
- Physician's notes.

10.3 HANDLING OF PATIENT TEMPORARY OR PERMANENT TREATMENT DISCONTINUATION AND OF PATIENT STUDY DISCONTINUATION

The IMP should be continued whenever possible. In case the IMP is stopped, it should be determined whether the stop can be made temporarily or permanently according to the context. Any IMP discontinuation should be fully documented in the e-CRF and source notes.

Pregnancy will lead to definitive treatment discontinuation in all cases.

